1.6 Rationale and hypotheses for the current study

The conclusion of reviews of research supports the need for further research in the form of randomised controlled trials, as do the recommendations from the studies cited above. The proposed study will be larger than previous studies and include assessment of change on the primary outcome measure of COPD specific health status (the COPD Assessment Test, CAT), immediately after a three-month programme of regular singing, and on further three month follow up. The primary research null hypothesis will be that: 'No change occurs in COPD-specific health status, following ten weeks of regular, weekly singing at the primary end point for the trial six months post-baseline.'

A particular challenge is establishing real-time records of patterns of respiratory function to test a secondary hypothesis that regular singing leads to change towards deeper breathing supported by the diaphragm. One technique which may do this is structured light plethysmography (SLP) where movements of the chest wall and abdomen can be recorded for individuals as participants' breath. A small, feasibility exercise assessing the value of this technique for the current study has been undertaken (see above). The supplementary null hypothesis will be that: 'No changes occur in key parameters (specified below) derived from structured light plethysmography reflecting movement of the chest and abdomen during breathing, following three months of regular singing, at the primary end point of the trial six months post-baseline.'

Further secondary hypotheses will be tested for potential changes three months post-baseline at the conclusion of the singing programme.

Singing and COPD protocol version 1, 18 December, 2018

As, following randomisation, participants will inevitably be fully aware of their allocation to singing group or control, the trial cannot be double-blinded. However, in follow-up assessments, the staff conducting the measurement procedures will be blind to trial allocation.

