- The Medway feasibility study (see above) showed an improvement on the CAT questionnaire of five points, more than twice the minimum clinical difference score of two. A change of five points represents a moderate effect size of approximately 0.5. If such a difference arises between the intervention and control groups in the proposed trial, where data is paired from pre-test and follow up, a sample size of 40 per group will be more than sufficient to give 90% power at a p-value of 5% (two-tailed) (Chan, 2003).
-
- The proposed study will assess participants immediately following the intervention and then after a further three months. No such follow-up has taken place in previous trials.

- The current study is a pilot and if the findings are encouraging the results could be subsumed into a larger multi-centre trial conducted in the same way.

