2.7 Randomisation

Following the assessments of the total sample at baseline, randomisation will be undertaken immediately, with stratification by sex and severity of COPD, and participants informed of their allocation. Use will be made of the 'Sealed Envelopes' professional randomisation service:

<https://www.sealedenvelope.com/>

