2.8 Data Analysis

The design of the trial is a 3 by 2 mixed anova design with time as the within subjects factor at 3 levels (baseline, end of intervention and follow-up) and Condition as the between subjects factor with 2 levels (singing vs. control). The primary outcome variable for the trial will be the COPD Assessment Test score. Additional secondary analyses will consider a range of additional health measures, together with spirometry, exercise and SLP parameters. We will also examine differences between the intervention and control groups on indicators of service use to determine potential cost-savings associated with reduced inhaler usage, consultations with health professionals and hospital admissions. Embedded within the trial will be a qualitative assessment of the participant experience and perceived benefits, together with an evaluation of the resources to support practice between singing sessions.

Quantitative data

Quantitative data will be analysed using IBM SPSS 24. Comparative analysis will take place to examine composition of the intervention and control groups at baseline to assess equivalence. Comparisons will be made between the intervention and control groups at two follow up points to

determine whether the intervention has resulted in significant change on the primary and secondary outcome measures, which allow for rejection of the null hypothesis that singing results in no change in functional status, health related quality of life, mental wellbeing and patterns of breathing. Appendix 7.11 provides a plan for the statistical analysis to be undertaken, and considerations of effect size and power, provided by the project statistical consultant [name].)

Qualitative data

For the qualitative data obtained from individual interviews, thematic analysis (Braun and Clarke, 2006) will be used to identify any consistent themes. The qualitative data will be analysed using QSR International's NVivo 11 software. Within NVivo, queries will be run to determine word frequencies within respondents' qualitative comments.

For the thematic analysis, this process has six phases:

- Familiarising yourself with your data: Transcribing data (if necessary), reading and re-reading the data, noting down initial ideas.
- Generating initial codes: Coding interesting features of the data in a systematic fashion across the entire data set, collating data relevant to each code.

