effect/analyses	expected difference	Notes	required N for minimum .80 power and alpha at .05 with moderate effect size d=.5		
anova - main effect of time	not relevant		34		
anova - main effect of condition	not relevant		86		
anova - interaction	significant		36		
anova - main effect of condition within T1	non significant		146	Bonferroni corrections included	sensitivity power analyses revealed that the minimum effect size detectable with power of .80 and sample size of 40 in each group is d=.68
anova- main effect of condition within T2	significant	the effect sizes of these two effects can be compared to test for prolonged effects of the intervention	146	Bonferroni corrections included	
anova - main effect of condition within T3	significant (but smaller than above)		146	Bonferroni corrections included	
anova - main effect of Time within Intervention Condition	significant		28		
anova - main effect of Time within TaU Condition	non significant		28		
anova - post hoc on main effect of Time within Intervantion Condition	significant between T1 and T2 but possibly disappearing between T2 and T3		39	Bonferroni corrections included	
anova - post hoc on main effect of Time within TaU Condition	not relevant		39	Bonferroni corrections included	

7.15 – Medway Singing and COPD Programme

The design of the singing programme is based on facilitator experience and participant feedback from singing for health projects conducted by the Sidney De Haan Research Centre over the past ten years. Each session will commence with physical and vocal warm-ups to prepare and protect the voice. These range in intensity and demand and are designed to provide a common focus, as well as encourage participants to learn to gain control of their breathing prior to singing.

Participants will be guided through a variety of songs, which gradually demand greater breath control and vocal production during the course of the singing sessions. Repertoire will include songs with short and long phrases, and a blended approach in each session will encourage confidence and breath-control. In addition, material will be utilised which encourages strong diction and vocal projection, both of which require consideration of breath control and management. Potential limitation in vocal range will be carefully addressed, with consideration given to the key and notation range in each song.

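### The six-month between-arm CAT test leaves out baseline CAT and the stratification factors; adjusting for them would gain power at almost no cost

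*Protocol*

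**What the plan says.** Protocol section 1.6 sets the null hypothesis for CAT "at the primary end point for the trial six months post-baseline". Sections 2.1, 2.8 and 7.14 all describe a 3 by 2 mixed ANOVA with two factors, Condition and Time. Baseline is one of the three levels of Time.

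Section 7.14 then lists the effects to be tested, each with a sample size under the column "required N for minimum .80 power and alpha at .05 with moderate effect size d=.5". The between-arm test at the primary time point is "anova - main effect of condition within T3", with N = 146 and the note "Bonferroni corrections included". The same table gives d = .68 as the smallest effect detectable with 80% power at 40 per group. The Time by Condition interaction is a separate row with N = 36.

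Section 2.7 randomises "with stratification by sex and severity of COPD", and section 2.6 collects CAT from all participants at baseline. Neither sex nor severity appears in any listed analysis, and no row carries a covariate.

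**The concern.** The T3 simple effect is a two-sample comparison of raw scores. A chance difference between arms in baseline CAT passes into it in proportion to r, and the between-patient variation that baseline CAT would explain stays in the standard error. The row testing Condition within T1 does not help, because a non-significant baseline test corrects nothing.

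The interaction does use baseline, but it is an omnibus test over three visits and does not estimate the arm difference at six months. Its baseline-to-T3 contrast is a difference in change scores, which is less precise than adjustment unless r is close to 1.

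Leaving out sex and severity also means that the standard error does not reflect any balance gained by stratifying.

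Section 2.2 sets the sample size by resources and discusses the ethics of an under-powered trial. The T3 row asks for 146 participants and 80 are expected. Precision that needs no further recruitment therefore matters here.

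**Working it through.** **Inputs.** 40 completers per arm (section 2.2); d = .5 (section 7.14); 5 CAT points taken as d of about 0.5, so SD of about 10 (section 2.2); feasibility CAT data of n = 21, means 25 and 20, paired t = 2.75 (section 1.5). The correlation r between baseline and T3 CAT is not stated and is an assumption.

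**The plan's own figures.** With a noncentral-t two-sample calculation and no covariate, one-sided alpha .016 (equivalent to two-sided of about .031) gives total N = 146 and a smallest detectable d of .678, matching the stated 146 and .68. Two-sided .05 gives N = 128 and two-sided .05/3 gives N = 172; neither matches. So the T3 row was sized without a covariate, at an alpha stricter than two-sided .05.

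**Plausible r.** SD of change = 5 × √21 / 2.75 = 8.33. With SD = 10, r = 1 − 8.33² / (2 × 10²) = .65. This is weak evidence:
- The 95% interval for the SD of change (6.37 to 12.03) gives r from .80 down to .28.
- SD = 8 instead of 10 gives r = .46.
- The data span about three months, while T3 is at six.

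The main range shown is therefore .5 to .7, with .3 as a low case.

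**Variance factors** relative to the raw T3 comparison: change score 2(1 − r); baseline-adjusted 1 − r². At r = .5 these are 1.00 and .75. At r = .65 they are .70 and .58.

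**Power.** The noncentrality is .5 × √(40/2) / √(1 − r²). This is 2.24 with no covariate, 2.58 at r = .5, 2.94 at r = .65 and 3.13 at r = .7. One further degree of freedom is spent on baseline.

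| Analysis, n = 40 per arm, d = .5 | Two-sided .05, no Bonferroni | One-sided .016 (reproduces 146 and .68) |
|---|---|---|
| Raw T3 comparison | 60% | 52% |
| Adjusted, r = .3 | 64% | 57% |
| Adjusted, r = .5 | 72% | 65–66% |
| Adjusted, r = .65 | 83% | 77–78% |
| Adjusted, r = .7 | 87% | 83% |

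Where a range is given, the lower end uses two-sided .031.

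**Against a change score** at two-sided .05: 60% for the change score and 72% adjusted at r = .5; 75% and 83% at r = .65; 81% and 87% at r = .7.

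**Equivalent sample size.** 40 / (1 − r²) gives about 53 unadjusted completers per arm at r = .5, 69 at r = .65 and 78 at r = .7.

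**Cost in degrees of freedom.** Spending four more on sex and severity leaves power at 72% (r = .5) and 83% (r = .65).

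**The case against.** A reader might infer that the plan ignores baseline CAT altogether, and that power is 60% where 83% is available. The documents do not support this, for four reasons.

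- Baseline is a level of Time, and the interaction, which the plan expects to be significant, uses it. The omission concerns the simple effects at T2 and T3. Measured against a change score, the gain is about 8 to 12 points at r = .65 and r = .5.
- The 60% figure is at two-sided .05. The T3 row includes a Bonferroni correction, and at the alpha that reproduces its figures power is about 52%.
- The 83% figure rests on r = .65, back-calculated from 21 patients, whole-number means and an approximate effect size. At r = .3 adjustment reaches only 64%.
- All these figures take a 5-point between-arm difference at T3. Section 7.14 expects the T3 effect to be smaller than at T2. With 4 points, SD 10 and r = .65, power at two-sided .05 is about 64% adjusted (42% unadjusted). At the 2-point clinical threshold it is about 21% (14% unadjusted).

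It is also fair to say that the unadjusted comparison is unbiased under randomisation, that omitting the strata tends to make the standard error conservative, and that the protocol calls the trial a pilot and discloses d = .68. These arguments limit the size and severity of the point. They do not remove it: adjustment raises power over the raw T3 comparison and the change score at every r shown.

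**Conclusion.** The point holds as an efficiency matter. The only listed between-arm test at the primary end point omits a strong candidate covariate and both stratification factors. For r of .5 to .7, 40 per arm and d = .5, adjusting for baseline CAT adds about 12 to 27 points of power to the raw comparison at two-sided .05, and about 13 to 30 points at the plan's own alpha.

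These gains depend on the assumed r and effect size, neither of which the protocol establishes for six months. They come from baseline CAT alone: the document gives nothing from which to quantify a gain from sex and severity, and the case for including those is that the analysis should match the randomisation. A reader might go further and call the planned test invalid, but nothing in the document supports that. This is a free improvement that should be made, not a fault that invalidates the trial.

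**What to change.** In section 7.14, and correspondingly in section 2.8, replace the simple-effect ANOVAs of Condition within T2 and within T3 with a linear model of follow-up CAT on arm, baseline CAT, sex and COPD severity stratum. Report the adjusted mean difference with its 95% confidence interval, with T3 as the primary result. Treat the other continuous outcomes in the same way, each with its own baseline value. If power is restated, give the alpha and the assumed r with it.

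The cost is a change of wording made before outcome data are seen, and about three to five residual degrees of freedom depending on the number of severity strata. No further data collection is needed, because baseline CAT and both stratification factors are already available before randomisation.

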7.16 Interview Schedules

Singing Group Participant Interview Schedule

Introduce yourself and thank the participant for agreeing to be interviewed. Check that they are happy to be recorded. Double check that the recorder is working!

Are you happy for this interview to be recorded? It will be completely confidential and the recording will be deleted at the end of the project. If yes:

Could you please give your name and the group you are attending for the purposes of this recording? If no:

Would you mind if I took a few brief notes as we talk? I will type these up later and let you check that you are happy with them as a record of our conversation.

1. Looking back, could you tell me how you got to hear about the project and why you were interested to join? **Card: Joining the project**
2. You were randomly allocated to the singing condition in the trial. Could you tell me how you felt about that? **Card: Singing condition**
3. More generally, could you tell me about your lung problem – how it started and what effects it has had on your life? **Card: Your lungs**
4. What help have you received in managing your condition? **Card: Help with your lungs**
5. Going back to this project, in terms of your physical health and your lungs, has being part of the singing group made any difference to you?
 - a. Has it made a difference for your breathing? **Card: Difference breathing?**
 - b. Has it made a difference to how active you are? **Card: Difference activity?**
 - c. Has it affected the support you have needed from your GP, the surgery and other health services? **Card: Difference support?**
 - d. Has it affected your use of medication? **Card: Difference medication?**

With each of these aspects prompt the participant to give more information if appropriate

6. Has the group made any difference to your mental and social wellbeing and health? In what ways? **Card: Mental and social wellbeing**
7. Have there been any aspects of the group and the singing activities that you haven't enjoyed or could have been improved? **Card: Improvements?**
8. Could you tell me how you got on with using the singing resource to practise at home between sessions, and the diary? **Card: Singing resource and diary**
9. We have evaluated this project by asking participants to complete lung function and exercise tasks and also complete questionnaires. Do you have any views on how we have tried to assess the project? **Card: Evaluation of project**

10. Do you have anything else you would like to add about your involvement in this project or any questions for me?

Thank the participant again for their help. Say that following the completion of the project a report will be prepared and they will receive a copy.

Control Group Participant Interview Schedule

Introduce yourself and thank the participant for agreeing to be interviewed. Check that they are happy to be recorded. Double check that the recorder is working!

Are you happy for this interview to be recorded? It will be completely confidential and the recording will be deleted at the end of the project. If yes:

Could you please give your name and the group you are attending for the purposes of this recording? If no:

Would you mind if I took a few brief notes as we talk? I will type these up later and let you check that you are happy with them as a record of our conversation.

1. Looking back, could you tell me how you got to hear about this project and why you were interested to join? **Card: Joining the project**
2. Could you tell me how you felt about being allocated to the control condition in the trial rather than the singing group? **Card: Being in the control condition**
3. More generally, could you tell me about your lung problem – how it started and what effects it has had on your life? **Card: Your lungs**
4. What help have you received in managing your condition? **Card: Help with your lungs**
5. Going back to the study, over the course of the project, have you noticed any differences in your health and wellbeing
 - a. Have you noticed a difference for your breathing? **Card: Difference breathing?**
 - b. Has there been a change in how active you are? **Card: Difference activity?**
 - c. Has there been a change in the support you have needed from your GP, the surgery and other health services? **Card: Difference support?**
 - d. Has there been a change in your use of medication? **Card: Difference medication?**

With each of these aspects prompt the participant to give more information if appropriate

6. We have evaluated this project by asking participants to complete lung function and exercise tasks and also complete questionnaires. Do you have any views on how we have tried to assess the project? **Card: Evaluation of project**

7. Do you have anything else you would like to add about your involvement in this project or any questions for me?

Thank the participant again for their help. Remind them that they will shortly have the opportunity to join a singing group. Say that following the completion of the project a report will be prepared and they will receive a copy.

7.17 Diary for recording of practice of singing at home

Diary for recording of practice of singing at home

Text and layout of a diary for participants to use is given below. This will be designed to form an attractive A5 booklet with one page per session.

Name _____

We would like you to keep a simple record of the practice you have done at home between sessions, and comment on the singing programme.

Please record whether you attended the session indicated, followed the practice video after the session and which songs you sang along to, plus any other activities you engaged in related to the singing programme.

	Did you attend this session?	Did you practise after the session as recommended?	What songs did you sing at home after the session?	How much time did you spend at home on exercises and singing?	Any other comments?
Session 1					
Session 2					
Session 3					
Session 4					
Session 5					
Session 6					
Session 7					
Session 8					
Session 9					
Session 10
